Appendix E Collection, Storage, and Shipment of Bioanalytical Samples

Instructions for Processing of Plasma Samples for Pharmacokinetic Analysis of Esomeprazole

- 1. Collect 6 mL of venous blood for the plasma into a chilled Becton-Dickinson Vacutainer. All esomeprazole blood samples should be collected into vacutainers containing K₂EDTA.
- 2. Gently invert the vacutainer several times to mix the additive with the collected blood prior to centrifugation and place immediately on ice.
- 3. Centrifuge the vacutainers for 10 minutes at approximately 1100 to 1300 (relative centrifugal force [RCF]) at 4°C. Note: if using a collection device other than Becton-Dickinson, refer to manufacturer's instruction for proper centrifugation force and time.
- 4. Immediately following centrifugation, gently remove plasma from the packed cells. To ensure a more homogeneous sample, all plasma should first be transferred into 1 aliquot. From there, split the plasma evenly between the 2 aliquots. A minimum of approximately 1 mL needs to be obtained for each sample. Labeling or manifest to the bioanalytical laboratory should include protocol number (Esomeprazole_1001), sample matrix (ie, plasma) enrollment number, period, profile day (optional) and nominal time, and either "SET 1" (for original sample) or "SET 2" (for duplicate sample).
- 5. Cap the labeled storage tubes and freeze the plasma samples immediately at approximately -20°C or lower until shipment to (vendor name, city, state/country). No more than 45 to 60 minutes will elapse between blood collection and freezing the plasma sample.

Shipping of Plasma Samples

The following instructions are recommended unless they differ from the site's SOPs for labeling, packaging, or shipping of pharmacokinetic samples.

- 1. Biological samples (ie, plasma) should be shipped on dry ice to prevent thawing during transit. Samples should be shipped only on Monday, Tuesday, or Wednesday, and at least 2 days prior to a national holiday, in order to minimize the possibility of samples in transit over a weekend or holiday. If duplicate samples are to be shipped, send SET 1 samples and await confirmation of arrival before shipping the duplicate SET 2 samples.
- 2. Before shipping, make sure the sample tubes are tightly sealed. Separate each subject's samples as follows:
- 3. Separate the duplicate SET 2 samples from the SET 1 samples.
- 4. Place SET 1 samples for each subject into self-sealing bag (eg, Ziploc) containing additional absorbent material.
- 5. Using a permanent marker, write the 4-digit {randomization sequence/enrollment} number, sample matrix (ie, plasma), number of samples, and "SET 1" on each self-sealing bag.
- 6. Place the bags of individual subject's samples into a larger plastic bag so that samples are double bagged. Duplicate SET 2 samples should be returned to the freezer for storage.

Esomeprazole	
Study No. Esomeprazole-1001	Page 70 of 71
Protocol	07 March 2017

Repeat steps 3 through 6 above when preparing duplicate samples for shipment, except self-sealing bags should be marked "SET 2."

- 7. An inventory of individual samples should accompany each shipment and should include the Sponsor's name (Takeda), study drug (esomeprazole), protocol number (Esomeprazole-1001), investigator's name, sample type (ie, plasma), subject randomization/enrollment number, period, nominal collection day and time, and intended sample storage conditions. When duplicate SET 2 samples are being shipped, make a copy of the original SET 1 sample inventory and mark as "SET 2." Place the inventory paperwork into a large self-sealing bag. SET 1 samples will be shipped first on dry ice, followed by shipment of duplicate SET 2 samples have been received by the analytical laboratory.
- 8. For sample packing, utilize dry ice generously (eg, 20-25 pounds per day of transit) to safeguard against longer than expected shipping times and delays. Use newspaper or other material to insulate the double-bagged samples from direct contact with the dry ice. Place the sample bundles into a Styrofoam container (or other suitable container) and fill the excess space with dry ice slabs or ice pellets (preferably the latter). Make a note of the estimated weight of the dry ice used per shipping container.
- 9. Place the inventory paperwork (in a large self-sealing bag) on top of the dry ice in the Styrofoam container. Place the lid on the Styrofoam container and seal completely with strapping tape. Place the Styrofoam container in a cardboard shipping carton and seal securely with strapping tape.
- 10. Mark the outside of shipping carton(s) with a tally number (eg, 1 of 5, 2 of 5).
- 11. Affix an address label to each shipping carton. Complete the address label with the following information:

12. Affix a carbon dioxide label on each carton, specifically:

3.0 LIST OF ABBREVIATIONS

%CV	percent coefficient of variation
λ_z	terminal dispostion rate constant
AE	adverse event
ANOVA	analysis of variance
AUC∞	area under the plasma concentration-time curve from time 0 to infinity
AUCt	area under the plasma concentration-time curve from time 0 to the time of last quantifiable concentration
BMI	body mass index
C _{max}	maximum observed plasma concentration
CI	confidence interval
CL/F	apparent clearance after extravascular administration
ECG	electrocardiogram
LLOQ	lower limit of quantification
MedDRA	Medical Dictionary for Drug Regulatory Activities
РК	pharmacokinetic(s)
PT	preferred term
PTE	pretreatment event
SD	standard deviation
SAE	serious adverse event
SI	International System of Units
SOC	system organ class
$t_{1/2z}$	terminal elimination half-life
t _{max}	time to reach C _{max}
TEAE	treatment-emergent adverse event
WHODrug	World Health Organization Drug Dictionary

4.0 **OBJECTIVES**

4.1 **Primary Objectives**

To determine the bioequivalence of esomeprazole 40 mg tablets and capsules.

4.2 Secondary Objectives

Not applicable.

4.3 Additional Objectives

To determine pharmacokinetic (PK) parameters for each formulation.

4.4 Study Design

This is a phase 1, randomized, open-label, 2-way cross-over study in healthy adult male and female subjects aged 18 to 55 years, inclusive, to evaluate the bioequivalence of a single oral dose of esomeprazole 40 mg capsules (reference [A]) and esomeprazole 40 mg tablets (test [B]).

It is estimated that 52 subjects will be needed to ensure that 48 subjects complete both periods. Screening for potential subjects will occur between 28 and 2 days prior to Day 1. On Day -1, subjects' eligibility will be reconfirmed and eligible subjects will be randomized in a 1:1 ratio to 1 of 2 sequences (AB or BA), which defines the order in which they will receive esomeprazole regimens in Periods 1 and 2. In both periods, subjects will fast for 10 hours prior to study drug administration and refrain from eating until 4 hours after drug administration. Each period will be separated by a minimum 6-day washout period. Blood samples for PK analysis will be drawn up to 10 hours after study drug administration on Day 1 in each period. Subjects will be confined to the phase 1 unit from Day -1 until the end of all assessments on Day 1 of each period.

Given that esomeprazole is a marketed product with a well-characterized safety profile, this study does not include a follow-up evaluation period. In total, the period of evaluation is expected to be a maximum of 36 days (assuming a washout period of 6 days), including the Screening Period.

A schematic of the study design is shown in Figure 4.a. A schedule of assessments is listed in Appendix A.

Pretreatment Period Period 1 (a) Period 2 (a) Single Washout Single Dose Checkout Check-in Checkout Screening (b) Check-in Dose and (d) and PK (c) PK (c) Days -28 to -Day -1 Day 1 Day 1 Day 2-6 Day -1 Day 1 Day 1 2 Confinement Confinement

Figure 4.a Schematic of Study Design

(a) Subjects will be admitted to the clinic on Day -1 of each period. On Day 1, subjects will be randomized to 1 of 2 sequences of esomeprazole tablet and capsule. Subjects will be discharged from the clinic on Day 1 after dosing and the completion of all scheduled procedures.

(b) For clinical laboratory tests that are required to be taken under fasting conditions, the subject will be asked to return to the unit at a later date under fasting conditions.

(c) PK samples at 0 (predose), and at 0.33, 0.66, 1, 1.33, 1.66, 2, 2.33, 2.66, 3, 3.5, 4, 4.5, 5, 6, 7, 8, 9, and 10 hours postdose.

(d) Minimum 6-day washout between doses. Day -1 of Period 2 could be the sixth day of washout.

5.0 ANALYSIS ENDPOINTS

5.1 Primary Endpoints

The primary endpoints for this study are the PK parameters derived from the plasma concentrations of esomeprazole 40 mg administered via capsule and tablet after a single dose, which include:

- area under the concentration-time curve from time 0 to infinity (AUC_{∞})
- area under the concentration-time curve from time 0 to time t (AUC_t)
- maximum observed concentration (C_{max})

5.2 Secondary Endpoints

Not applicable.

5.3 Additional Endpoints

Additional endpoints for this study are the PK parameters derived from the plasma concentrations of esomeprazole 40 mg administered via capsule and tablet after a single dose, which include:

- time of first occurrence of Cmax (tmax)
- terminal disposition phase half-life (t1/2z)
- apparent clearance after extravascular administration, calculated using the observed value of the last quantifiable concentration (CL/F)
- apparent volume of distribution during the terminal disposition phase after extravascular administration, calculated using the observed value of the last quantifiable concentration (Vz/F)
- terminal disposition phase rate constant (λz)
- lag time to first quantifiable concentration (tlag)

6.0 DETERMINATION OF SAMPLE SIZE

The sample size for this study is estimated at 52, which provides an allowance for 4 dropouts.

The sample size was estimated based on variability data from a previous study, using a percent coefficient of variation (%CV) of 28% as the intrasubject variation for the natural logarithm of C_{max} and the assumed true ratio of 0.95 for tablet over capsule. Given the above information, a sample size of 52 subjects provides at least 90% power for concluding bioequivalence for C_{max} and the power for AUCs is greater than 90%.

7.0 METHODS OF ANALYSIS AND PRESENTATION

7.1 General Principles

Continuous data will be summarized using descriptive statistics, including the number of subjects, mean, standard deviation (SD), median, minimum, and maximum. The coefficient of variation (%CV) and geometric mean will be included in the summary of continuous data where indicated. Categorical data will be summarized as the number and percentage of subjects in each category.

Arithmetic means, geometric means, and medians will be presented to 1 more decimal place than the recorded data, and SDs will be presented to 2 more decimal places than the recorded data, where appropriate. Where applicable, confidence intervals about a parameter estimate will be presented using the same number of decimal places as the parameter estimate and p-values will be rounded to 3 decimal places prior to assessment of statistical significance.

All study-related raw data for enrolled subjects, including derived data, will be presented in data listings. In addition, the actual day relative to the first dose will be presented, where applicable.

All statistical analyses will be performed using the SAS System® Version 9.4.

7.1.1 Study Definitions

There are no study-specific definitions.

7.1.2 Definition of Study Days

Study Day 1 is defined as the date of the first dose of study drug, as recorded on the electronic case report form (eCRF) dosing page. Other study days are defined relative to Study Day 1, with Day 1 being Study Day 1 and Day -1 being the day prior to Study Day 1. Study days prior to the first dose of study drug will be calculated as: {date of assessment/event – date of first dose of study drug}. Study days on or after the first dose of study drug will be calculated as: {date of assessment/event – date of first dose of assessment/event – date of first dose of study drug + 1}.

All protocol-specified study visit dates are defined relative to Study Day 1.

7.1.3 Definition of Study Visit Windows

There will be no visit windowing.

7.1.4 Conventions for Missing Adverse Event Dates

There will be no imputation of incomplete or missing adverse event dates.

7.1.5 Conventions for Missing Concomitant Medication Dates

There will be no imputation of incomplete or missing concomitant medication dates.

7.1.6 Conventions for Missing Data

There will be no imputation of incomplete or missing data.

Plasma concentrations that are below the lower limit of quantification (< LLOQ) will be treated as zero in the summarization of concentration values and derivation of PK parameters.

7.2 Analysis Sets

The following analysis sets will be used for analysis and presentation of the study data:

- Randomized Set: The randomized set will consist of all subjects who are randomized.
- Safety Analysis Set: The safety analysis set will consist of all subjects who are randomized and received at least 1 dose of study drug. Subjects in this analysis set will be used for demographic, baseline characteristics, and safety summaries.
- Pharmacokinetic Set: The PK set will consist of all subjects who received at least 1 dose of study drug and have at least 1 measurable plasma concentration.

If any subjects are found to be noncompliant in dosing schedule or with incomplete data, a decision will be made on a case-by-case basis as to their inclusion in the analysis but will be presented in the subject listings.

Number of subjects in each analysis set will be tabulated by randomization sequence and overall.

7.3 Disposition of Subjects

Study Information, including date of first subject signing Informed Consent Form (ICF), date of first/last study drug, date of last subject's last visit/contact, date of last subject's last procedure for collection of data for primary endpoint, Medical Dictionary for Drug Regulatory Activities (MedDRA) Version, World Health Organization Drug Dictionary (WHODrug) Version, and SAS Version, will be tabulated.

The eligibility of subjects will be summarized, along with the primary reasons of screen failure as recorded in eCRF.

Number of subjects randomized will be tabulated by randomization sequence (ie AB or BA) and overall.

Disposition of all enrolled subjects will be tabulated. Categories will include:

- Subjects who were randomized but not treated
- Subjects who completed the study
- Subjects who prematurely discontinued study

Primary reasons for discontinuing study, as entered on the eCRF will be tabulated.

Esomeprazole-1001	Page 12 of 23
Statistical Analysis Plan Final	01 June 2017

7.4 Demographic and Other Baseline Characteristics

Demographic and study baseline characteristics, including age at informed consent, gender, ethnicity, race, height (cm), weight (kg), body mass index (kg/m^2), smoking status, alcohol use, caffeine/xanthine consumption, and female reproductive status, will be summarized by sequence and overall.

There will be no inferential analysis of demographic and baseline characteristics.

7.5 Medical History and Concurrent Medical Conditions

Medical history is defined as significant conditions or diseases that resolved at or prior to the time of informed consent. Concurrent medical conditions are defined as significant conditions or diseases that are present at signing of informed consent.

Medical history and concurrent medical conditions will be coded using the MedDRA coding system.

Medical history and concurrent medical conditions will be listed by site and subject number.

There will be no summary or inferential analysis of medical history and concurrent medical conditions.

7.6 Medication History and Concomitant Medications

Medication history information includes any medication relevant to eligibility criteria stopped at or within 28 days prior to signing of informed consent. Concomitant medication is any drug given in addition to the study drug, taken at any time from signing of informed consent through the end of study.

Medication history and concomitant medications will be coded using the WHODrug.

Listings for medication history and concomitant medications will be produced by site and subject number.

There will be no summary or inferential analysis of medication history and concomitant medications.

7.7 Study Drug Exposure and Compliance

All doses of study medication will be administered during confinement. Dosing data, including dosing time will be provided by subject and visit in the listings.

7.8 Efficacy Analysis

Not applicable.

7.9 Pharmacokinetic/Pharmacodynamic Analysis

7.9.1 Pharmacokinetic Analysis

The schedule for blood samples for PK analysis of Esomeprazole is listed in Table 7.a.

The concentration of esomeprazole in plasma will be summarized by formulation over each scheduled sampling time point using descriptive statistics (arithmetic mean, SD, CV%, median, minimum and maximum). Individual plasma concentration data versus time will be presented in a data listing.

In addition, the figures for mean plasma concentrations of esomeprazole versus time (linear and semi-log scale) will be generated.

Descriptive statistics (N, mean, SD, CV%, median, minimum and maximum) will be used to summarize the PK parameters for Esomeprazole by formulation. In addition, geometric mean will be computed for PK parameters. The PK parameters of Esomeprazole are listed in Table 7.b.

Table 7.a Collection of Blood Samples for Pharmacokinetic Analysis

Analyte	Matrix	Dosing Day	Scheduled Time (hours)
Esomeprazole	Plasma	1	Predose, 0.33, 0.66, 1, 1.33, 1.66, 2, 2.33, 2.66, 3, 3.5, 4, 4.5, 5, 6, 7, 8, 9, and 10 hours

Symbol/Term	m Definition	
Plasma		
AUCt	Area under the concentration-time curve from time 0 to time t	
AUC∞	Area under the concentration-time curve from time 0 to infinity, calculated using the observed value of the last quantifiable concentration.	
C_{max}	Maximum observed concentration.	
CL/F	Apparent clearance after extravascular administration, calculated using the observed value of the last quantifiable concentration.	
λz	Terminal disposition phase rate constant.	
t _{1/2z}	Terminal disposition phase half-life.	
tlag	Lag time to first quantifiable concentration.	
t _{max}	Time of first occurrence of C _{max}	
V _z /F	Apparent volume of distribution during the terminal disposition phase after extravascular administration, calculated using the observed value of the last quantifiable concentration.	

Table 7.bPlasma PK Parameters

Esomeprazole-1001	Page 14 of 23
Statistical Analysis Plan Final	01 June 2017

Box plots for Cmax and AUC ∞ will be generated by formulation.

The bioequivalence between Esomeprazole capsules (Reference - Regimen A) and Esomeprazole tablets (Test - Regimen B) will be assessed for the natural logarithms of AUCt, AUC ∞ , and Cmax using analysis of variance (ANOVA) models. The models will include regimen, period, and sequence as fixed effects and subject nested within sequence as a random effect. Within the ANOVA framework, point estimates and their 90% CIs for the ratio of AUCs and Cmax central values between Esomeprazole capsules and tablets will be presented. Bioequivalence between tablet and capsule will be claimed if the 90% CI for the ratio is within the bioequivalence criteria of 0.80 to 1.25.

All pharmacokinetic parameters calculated will be provided in a listing.

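### Does the claim rule leave open whether Cmax, AUCt and AUC∞ must all pass?

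*SAP*

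**What the plan says.** SAP 5.1 and Protocol 5.2.1 list AUC∞, AUCt and Cmax together as primary. SAP 7.9.1 says that bioequivalence "will be assessed for the natural logarithms of AUCt", AUC∞ and Cmax, with an ANOVA model for each. It continues: "point estimates and their 90% CIs for the ratio of AUCs and Cmax central values between Esomeprazole capsules and tablets will be presented". The decision rule comes next: "Bioequivalence between tablet and capsule will be claimed if the 90% CI for the ratio is within the bioequivalence criteria of 0.80 to 1.25". Protocol 2.0 and 13.1.3 have the same structure and the same singular wording. None of these places uses a word such as all, each or any.

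SAP 6.0 (and Protocol 13.3) takes an intrasubject CV of 28% for Cmax and "the assumed true ratio of 0.95 for tablet over capsule". It concludes that "a sample size of 52 subjects provides at least 90% power for concluding bioequivalence for C_{max} and the power for AUCs is greater than 90" per cent. It gives no CV for the AUCs and no power for meeting the criterion on all three parameters. SAP 4.4 expects 48 of the 52 subjects to complete both periods, and Protocol 7.6 says that withdrawn subjects are not replaced.

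**The concern.** There is one product-level conclusion and there are three confidence intervals, but the rule speaks of one interval and one ratio. Read literally, it does not say what is concluded if the AUCs pass and Cmax fails.

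The two possible readings differ greatly. If all three must pass, the chance of a false claim is at most 5% with no adjustment of alpha, because the claim cannot be made unless the non-equivalent parameter also passes. If any one were enough, a tablet whose Cmax sits on the limit could be declared bioequivalent on its AUC.

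The second worry is power. If all three must pass, the probability of making the claim is the joint power. That cannot exceed the lowest single-endpoint power and may be below it, so a reader could take the 90% in the sample-size section as the chance of overall success when it is not.

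**Working it through.** **1. The stated Cmax power.** Inputs from SAP 6.0: CV 28%, true ratio 0.95, N = 52. From SAP 7.9.1: 90% CI, limits 0.80 to 1.25.

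- σ_w = √ln(1 + 0.28²) = √0.0755 = 0.275.
- SE of the log ratio = σ_w √(2/N): 0.0539 at N = 52 and 0.0561 at N = 48.
- Distance from ln 0.95 to ln 0.80 = −0.0513 + 0.2231 = 0.1718, which is 3.19 SE at N = 52 and 3.06 SE at N = 48.
- Exact power of the two one-sided tests, with N − 2 degrees of freedom: **93.3%** at 52 and **91.5%** at 48.

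Both satisfy the stated minimum of 90%. If 0.28 is used directly as the log-scale SD, the results are 92.5% and 90.5%.

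**2. The stated AUC power.** This cannot be reproduced without a CV. At ratio 0.95, power is above 90% for any AUC CV below about 30% at N = 52, or about 29% at N = 48. The statement is therefore true unless AUC is more variable than Cmax.

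**3. Power for all three.** Assumptions not in the documents: AUC CV 15–28%, AUC ratios 0.95, correlation 0.99 between AUCt and AUC∞, and 0.3–0.9 between Cmax and the AUCs. The 0.99 is reasonable: Protocol 6.2 gives a mean half-life of about 1 hour and sampling runs to 10 hours, so the extrapolated tail is usually small. The joint figures are simulated (200,000 trials per setting).

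| AUC CV | Each AUC alone, N = 52 | All three, N = 52 | All three, N = 48 |
|---|---|---|---|
| 15% | 100% | 93% | 91–92% |
| 20% | 99.7% | 93% | 91% |
| 22% | 99.0% | 92–93% | 90% or more |
| 25% | 96.9% | 90–93% | 88–91% |
| 28% | 93.3% | 87–91% | 84–88% |

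A check that needs no correlation is the lower bound 1 minus the sum of the failure probabilities:

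- AUC CV 20%, N = 52: 1 − 0.0670 − 2 × 0.0033 = 92.6%.
- AUC CV 20%, N = 48: 1 − 0.0855 − 2 × 0.0055 = 90.4%.
- AUC CV 25%, N = 52, the two AUCs passing or failing together: 1 − 0.0670 − 0.0311 = 90.2%.

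The third agrees with the low end of the table. If the AUCs are not assumed to move together, it falls to 1 − 0.0670 − 2 × 0.0311 = 87.1%.

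**4. What the any-one reading would cost.** With Cmax truly at 0.80, both AUCs at 0.95, AUC CV 20% and N = 52 (Cmax–AUC correlation 0.7), an any-one rule makes the claim in 99.7% of trials and an all-three rule in 5.1%. With all three ratios at 0.80, an any-one rule errs in 14.2% of trials under independence and in about 8–10% in the correlated cases tried.

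**5. Which reading the text supports.** The subject of the rule is set one sentence earlier, as the ratio of the AUCs and Cmax, so the criterion applies to each of them. The sample-size section works the same way: it sizes the trial on Cmax and then confirms that the AUCs are covered. Under an any-one rule the easiest parameter would fix the sample size and Cmax would not matter. Nothing in either document points to an any-one rule.

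**The case for a change.** The strongest case for a change is that this is the decision rule for the only primary objective and should not rest on inference. Protocol 13.1.3 defers detail to the SAP, yet the SAP repeats the same singular sentence. A mixed result is possible, the wording would cost almost nothing to tighten, and the plan expects 48 completers, where joint power can fall to 84–88% if AUC is as variable as Cmax. If full independence is assumed, even between the two AUCs, it falls to 76%.

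Part of this stands. The rule does not say outright that all three must pass, the AUC power cannot be checked from the documents, and neither stated power is the probability of the overall claim.

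The rest does not carry. An unstated word is not permission to claim on one parameter. SAP 7.9.1 commits to presenting every estimate and interval, so a failing Cmax would be in plain view. The powers are labelled by endpoint, and neither is offered as the power of the overall claim. The figures clearly below 90% need an AUC CV near that of Cmax, or independence between two AUCs that share almost all of their area. The documents support neither, although without the cited variability source the first cannot be ruled out.

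**Conclusion.** No change is needed. Read in context, the rule requires the intervals for Cmax, AUCt and AUC∞ all to lie within 0.80 to 1.25. That reading holds the product-level error at 5% without adjustment. The 99.7% against 5.1% contrast measures the cost of a rule that the plan does not contain.

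No stated figure is wrong. Under the assumptions in the table, the chance of the overall claim stays at 90% or more with 52 subjects up to an AUC CV of 25%, and with 48 completers up to 22%. A shortfall needs a more variable AUC, and the documents give no figure either way. Writing out the rule or quoting a joint power would alter no estimate, interval, margin, sample size or conclusion. The report's author can make both points in a sentence.
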